# 6.7.5 Urinalysis

Urinalysis data will be summarised and listed.

Potentially clinically significant values will be defined as displayed in Table 3.

Table 3 Potentially clinically significant urinalysis values

Protocol lab parameter	SI Unit	PCS low	PCS High
(ACM lab parameter)			

Trial ID: LP0162-1325	Date: 20-May-2019	Version: 1.0
		Page 25 of 31

Erythrocytes	/HPF	N/A	> 3, >10, >25, >30
Leucocytes	/HPF	N/A	> 10
Casts (Hyaline casts)	/LPF	N/A	> 2
Casts (WBC casts)	/LPF	N/A	Few, Moderate, Many
Casts (RBC casts)	/LPF	N/A	Few, Moderate, Many
Casts (Waxy casts)	/LPF	N/A	Few, Moderate, Many
Casts (Granular casts)	/LPF	N/A	Few, Moderate, Many

PCS: potentially clinically significant; HPF: high power field; LPF: low power field; ULN: Upper limit of normal, i.e. upper limit of normal reference range.

#### 6.7.6 Staphylococcus aureus

Staphylococcus aureus colonization based on skin swab samples will be summarised and listed.

## 6.7.7 Pharmacokinetics and anti-drug antibodies

Pharmacokinetics and anti-drug antibodies data will be summarised and listed.

## 6.7.8 Biomarkers

The small panel biomarkers; periostin, DPP4, hBD2, TARC, IL-13, IL-17, IL-22, and IgE will be summarized and listed. Other potential biomarkers from the small panel will be presented in a separate report.

As described in the protocol the large panel biomarkers will be presented in a separate report.

## 6.7.9 Biopsy biomarkers

Skin biopsies will be taken at selected trial sites.

The Histology/immunohistochemistry markers; epidermal thickness, FLG, CD3, CD1a, and CD11c and gene expression analysis; IFN, IL-13, CCL17, CCL22, IL-17A, IL-22, S100A12, and LOR will be summarised and listed. All other skin biopsy markers will be presented in a separate report.

## 6.8 General Principles

#### 6.8.1 Baseline value

Unless otherwise specified, the baseline value is defined as the latest pre-dose assessment.

# 6.8.2 Definition of trial periods and date of permanent discontinuation of IMP

#### Date of permanent discontination of IMP

Defined for subjects who have a reason for permanent discontinuation of IMP recorded. Defined as date of early termination visit (if existing), otherwise date of the last visit, excluding safety follow-up and nominal Week 16 visit.

Exposure start

Date and time of first dose.

Exposure end (subjects not enrolled in short term extension)

Date of Week 52 visit (if existing) at time 23:59:00, otherwise date of permanent discontinuation of IMP (if existing) at time 23:59:00, otherwise date of last IMP administration at time 23:59:00.

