Prior to self-administration at home, the individual who will be administering the injections (i.e., the subject and/or the caregiver) will receive proper training (that is, at 3 dosing visits during open-label treatment after additional consent has been obtained) in SC injection technique and on procedures to be followed in the event of an emergency during or following home-use of tralokinumab. This training will be conducted by the unblinded HCP.

The subject and/or the caregiver must also undertake SC administration under HCP supervision on one or more occasions such that the HCP is satisfied with the individual's understanding and confidence of the procedure.

Subjects or their caregivers will only self-administer tralokinumab at home every 4 weeks, i.e., in weeks where no efficacy and safety assessments are scheduled (Panel 4 and Panel 5; see also Section 9.9.3). Where trial visits with efficacy and safety assessments are scheduled (every 4 weeks), tralokinumab injections will be administered at the trial site, preferably by the subject or their caregiver, alternatively by the unblinded HCP, when all assessments have been completed.

At each trial visit it will be recorded in the eCRF whether tralokinumab was administered by the subject or the unblinded HCP.

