#### Assignment of AEs to periods

An adverse event will be assigned to a given period (initial, maintenance, open-label or follow-up) if the start date is after the start date and before the end date of that period (see Section 6.8.2, Table 4).

For AEs with start day on the same day as the first dose was given, only AEs starting after the first dose was given will be considered treatment emergent and assigned to the initial treatment period.

AEs with start date on the same day as the first dose of maintenance treatment will be assigned to the initial or maintenance period depending on whether the AE started before or after the dose was given.

AEs with start date on the same day as the first dose of open-label treatment will be assigned to the previous treatment period (can be initial or maintenance) or assigned to the open-label period depending on whether the AE started before or after the dose was given.

AEs starting on the day of exposure end (as defined in Section 6.8.2) will be assigned to the last treatment period.

For handling of incomplete start dates of adverse events, see Section 6.8.3.

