#### Trial periods

The time from exposure start to exposure end will be divided into initial period, maintenance period and open-label period, and remaining time after exposure end will be assigned to the follow-up period as shown in Table 4 (ADaM variable APHASE). The ADaM variable APERIODC will indicate the latest treatment (initial, maintenance or open-label) at any given time point, thus not including a follow-up period (Table 5).

Trial ID: LP0162-1325	Date: 20-May-2019	Version: 1.0
		Page 27 of 31

ADUASE	Start of pariod	End of noniad (only if star	t data a
Table 4: Start a	nd end time of trial	periods (ADaM variable APH	IASE).

APHASE	Start of period	End of period (only if start date exists)
Initial	Exposure start	Date and time (minus 1 second) of first maintenance
period		dose (if existing)
		else
		Date and time (minus 1 second) of first open-label dose
		(if existing)
		else
		Exposure end
Maintenance	Date and time of	Date and time (minus 1 second) of first open-label dose
period	first maintenance	(if existing)
	dose (if existing)	else
		Exposure end
Open-label	Date and time of	Exposure end
period	first open-label	
	dose (if existing)	
Follow-up	Exposure end	Date of safety follow-up visit (if existing) at time
period 	(plus 1 second)	23:59:00
		else
		Date of last contact at time 23:59:00

1) Only applicable if date of last contact is not equal to date of exposure end.

APERIODC	Start of period	End of period (only if start date exists)
Initial period	Exposure start	Date and time (minus 1 second) of first maintenance
		dose (if existing)
		else
		Date and time (minus 1 second) of first open-label dose
		(if existing)
		else
		Date of last contact at time 23:59:00
Maintenance	Date and time of	Date and time (minus 1 second) of first open-label dose
period	first maintenance	(if existing)
	dose (if existing)	else
		Date of last contact at time 23:59:00
Open-label	Date and time of	Date of last contact at time 23:59:00
period	first open-label	
	dose (if existing)	

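### Without an early termination visit, the SAP ends the treatment period at the last attended visit, so an adverse event or death starting days after the last dose can be counted in follow-up

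*SAP*

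**What the plan says.** SAP 6.8.2 dates permanent discontinuation of IMP by a visit: "Defined as date of early termination visit (if existing), otherwise date of the last visit, excluding safety follow-up and nominal Week 16 visit". Exposure end outside the short-term extension is then "Date of Week 52 visit (if existing) at time 23:59:00, otherwise date of permanent discontinuation of IMP (if existing) at time 23:59:00". The last-dose date is used only when neither a Week 52 visit nor a discontinuation date exists. The extension has the same rule with Week 68. No days are added after the last dose.

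Under Table 4, "remaining time after exposure end will be assigned to the follow-up period as shown in Table 4", beginning one second after exposure end. SAP 6.7.1 places each adverse event by its start date: "An adverse event will be assigned to a given period (initial, maintenance, open-label or follow-up) if the start date is after the start date". Only an event starting on the very day of exposure end is kept in the last treatment period. SAP 5 evaluates follow-up events on a separate safety follow-up analysis set.

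Protocol 12.3.7.1 tests, for the initial treatment period, the percentages of subjects with adverse events and with related adverse events. It treats any event starting after first IMP use as treatment-emergent, with no upper time limit. Protocol 8.5 asks subjects who stop IMP to attend an early termination visit and lists death and loss to follow-up among the recorded reasons for stopping.

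**The concern.** The period to which an event belongs should depend on exposure. Here, for a subject who stops, it depends on whether a later visit was attended. A subject who dies between visits cannot attend one, and a subject who becomes ill after an injection and withdraws by telephone may not.

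For these subjects the treatment period can close on the day of the last injection, and an event a few days later is counted as a follow-up event. It then leaves the initial-period comparison, or the maintenance or open-label tables, and the treatment-period summaries of SAEs and deaths. A completer with the same event at the same interval after the last dose keeps it in the treatment period.

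**Working it through.** **The plan's own timing.** Protocol 9.2 puts the last dose at Week 50 (Week 66 in the extension), with the safety visit 16 weeks later. 50 + 16 = Week 66, and 66 − 52 = 14 weeks off treatment, as Protocol 7.1 states. For the extension, 66 + 16 = Week 82 and 82 − 68 = 14 weeks. The figures reproduce.

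**Post-dose time inside the treatment period.**
- Completer: exposure ends at Week 52 and the last dose is at Week 50, so (52 − 50) × 7 = 14 days. In the extension, (68 − 66) × 7 = 14 days.
- Subject without an early termination visit whose last visit was a dosing visit: 0 days beyond the dosing day.

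**One event under two attendance patterns.** Take a last dose and last scheduled visit at Week 8 (day 56) and an event starting on day 61.
- Early termination visit on day 70: exposure ends on day 70. Since 61 < 70, the event is in the initial period.
- No such visit: exposure ends on day 56 at 23:59. Since 61 > 56, the event is in follow-up.

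Dose, onset and drug exposure are identical in the two cases.

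**Is the drug still present?** Exclusion criterion 29 equates 16 weeks with 5 half-lives, so the half-life is 16 × 7 / 5 = 22.4 days. With single-exponential decline (an approximation), the fraction left after d days is 2^(−d/22.4): 86% at 5 days, 80% at 7 and 65% at 14.

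**Does another rule repair it?** SAP Table 5 (APERIODC) carries the latest treatment through to last contact and would keep the event with it. SAP 6.7.1 refers to Table 4, which does not.

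**Size in the initial period.** Arms of 585 and 195 are from Protocol 12.1. Assumptions, not in the documents: a fraction f = 5–10% stops before Week 16, on average at day 56; a fraction g = 25–100% of these have no early termination visit; each loses a full 14 days.
- Subjects = n × f × g. Tralokinumab: 585 × 0.05 × 0.25 = 7.3 to 585 × 0.10 × 1.00 = 58.5. Placebo: 2.4 to 19.5.
- Patient-years moved = subjects × 14 / 365.25. Tralokinumab: 0.28 to 2.24. Placebo: 0.09 to 0.75.
- Total patient-years = n × [(1 − f) × 112 + f × 56] / 365.25. Tralokinumab: 174.9 (f = 5%) or 170.4 (f = 10%). Placebo: 58.3 or 56.8.
- Share moved: 0.28/174.9 = 0.16% to 2.24/170.4 = 1.3%, the same in both arms because the same rates were assumed.

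One subject changes an arm's percentage by 1/585 = 0.17 points (tralokinumab) or 1/195 = 0.51 points (placebo), and then only if no other event already counts that subject.

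**Home use (open-label, selected countries).** Protocol 9.2: "Subjects or their caregivers will only self-administer tralokinumab at home every 4 weeks, i.e., in weeks where no efficacy and safety assessments are scheduled". Suppose a site visit at Week 24 (day 168), a home dose at Week 26 (day 182), no early termination visit, and the dose log handed in at the safety follow-up visit. If the home dose is not itself entered as a visit, exposure ends on day 168, which is 14 days before the last recorded dose.

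**The case against.** The strongest reply is that nothing disappears. Follow-up events have their own tables by treatment group (SAP 6.7.1), every SAE gets a narrative, and adverse events leading to withdrawal are tabulated and listed (Protocol 12.3.7.1). All of that stands. Four stronger readings are tempting, and the documents do not support them.

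- A reader might infer that a between-arm test of deaths or SAEs is compromised. Protocol 12.3.7.1 states tests only for the percentages with adverse events and with related adverse events. Deaths and SAEs are summarised, and it is those summaries that change.
- A reader might infer that discontinued subjects in general get no time after the last dose. Everyone who stops is asked to attend an early termination visit, and exposure then runs to it. A later attended visit without dosing also extends exposure. Zero days needs both no early termination visit and a last visit on the last dosing day.
- A reader might infer that any fatal event is moved. Assignment is by start date, so a fatal event that began on or before the last visit stays in the treatment period.
- A reader might infer that home use distorts a randomised comparison. It is open-label only. Home doses are transcribed at the next trial visit (Protocol 9.9.5), so a subject who never returns will generally have no recorded later dose.

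It is also fair that subjects lost to follow-up often have no later event to reassign, so the subject counts above overstate the events at issue. No difference between arms has been shown.

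**Conclusion.** The gap is real and narrow. For a subject who discontinues without an early termination visit, and whose last visit was the last dosing day, any event starting from the next day falls in follow-up. Attendance, not exposure, decides. No other SAP rule corrects this, and the protocol's open-ended definition of treatment-emergent would still count the event.

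Under the assumed rates the patient-time is small, at most about 1.3% per arm, and the overall percentage with any adverse event would hardly change. The point matters for rare events: deaths between visits, and serious events that prevent a return visit, where one or two cases determine what a treatment-period summary shows. The mechanism follows from the SAP's wording alone. The size rests on rates the documents do not give. The home-use inconsistency is secondary and needs a recorded later dose.

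**What to change.** Leave the date of permanent discontinuation as it is, because the efficacy estimands use it. Change only exposure end. For a subject without a Week 52 visit (Week 68 in the extension), define it as the later of:

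- (a) the date SAP 6.8.2 gives now, keeping its exclusion of the safety follow-up and nominal Week 16 visits; and
- (b) the last recorded IMP administration plus 14 days;

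capped at 23:59 on the date of death or last contact. Keep the existing data cut-off rule for subjects still in the extension at the first database lock. State what date of last contact means for a subject who died: the Table 4 footnote drops the follow-up period when that date equals exposure end.

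Carry the definition through both exposure-end paragraphs of SAP 6.8.2, Table 4, the adverse event assignment in 6.7.1, patient-years in 6.5, and the safety follow-up analysis set in Section 5, which restates exposure end. The maintenance rescue-medication summary in 6.3 also refers to the follow-up period and should be checked.

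The result is at least the completers' nominal 14 days unless death or last contact comes first. The windows will not be identical, since someone attending an early termination visit later than day 14 keeps the longer period. The cost is one derivation and a few consistent edits before unblinding. A few events and a little patient-time move from the follow-up to the treatment tables. No trial procedure changes.

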#### Exposure end (subjects enrolled in short term extension)

Date of Week 68 visit (if existing) at time 23:59:00, otherwise date of permanent discontinuation of IMP (if existing) at time 23:59:00, otherwise date of last IMP administration at time 23:59:00.

At DBL 1 all data up to and including LSLV, April 11, 2019 is included. For subjects ongoing at DBL 1 (i.e. subjects ongoing in short term extension), exposure end will be set to date of data cut-off April 11, 2019.

#### Trial periods

The time from exposure start to exposure end will be divided into initial period, maintenance period and open-label period, and remaining time after exposure end will be assigned to the follow-up period as shown in Table 4 (ADaM variable APHASE). The ADaM variable APERIODC will indicate the latest treatment (initial, maintenance or open-label) at any given time point, thus not including a follow-up period (Table 5).

Trial ID: LP0162-1325	Date: 20-May-2019	Version: 1.0
		Page 27 of 31

ADUASE	Start of pariod	End of noniad (only if star	t data a
Table 4: Start a	nd end time of trial	periods (ADaM variable APH	IASE).

APHASE	Start of period	End of period (only if start date exists)
Initial	Exposure start	Date and time (minus 1 second) of first maintenance
period		dose (if existing)
		else
		Date and time (minus 1 second) of first open-label dose
		(if existing)
		else
		Exposure end
Maintenance	Date and time of	Date and time (minus 1 second) of first open-label dose
period	first maintenance	(if existing)
	dose (if existing)	else
		Exposure end
Open-label	Date and time of	Exposure end
period	first open-label	
	dose (if existing)	
Follow-up	Exposure end	Date of safety follow-up visit (if existing) at time
period 	(plus 1 second)	23:59:00
		else
		Date of last contact at time 23:59:00

1) Only applicable if date of last contact is not equal to date of exposure end.

APERIODC	Start of period	End of period (only if start date exists)
Initial period	Exposure start	Date and time (minus 1 second) of first maintenance
		dose (if existing)
		else
		Date and time (minus 1 second) of first open-label dose
		(if existing)
		else
		Date of last contact at time 23:59:00
Maintenance	Date and time of	Date and time (minus 1 second) of first open-label dose
period	first maintenance	(if existing)
	dose (if existing)	else
		Date of last contact at time 23:59:00
Open-label	Date and time of	Date of last contact at time 23:59:00
period	first open-label	
	dose (if existing)	

## 6.8.3 Incomplete recordings

#### Adverse events

If the AE start day is missing, but AE start month and year are not missing, the following rules apply:

- If the year and month of the AE start is before the year and month of the exposure start, or if the AE end date is complete and before the exposure start, the AE will not be considered treatment emergent.
- If the year and month of the AE start is the same as the year and month of the exposure start, the AE will be considered treatment emergent and assigned to the initial treatment period, unless the AE has a complete end date which is before exposure start.
- If the year and month of the AE start is after the year and month of exposure start, it will be assumed that the AE started on the first day of the month and the AE will be assigned to the initial, maintenance, open-label or follow-up period accordingly.

If the AE start month is missing, but AE start year is not missing, the following rules apply:

- If the year of the AE start is before the year of the exposure start, or if the AE end month is not missing and before the month of the exposure start, or if the AE has a complete end date which is before the exposure start date, the AE will not be considered treatment emergent.
- If the year of the AE start is the same as the year of the exposure start, the AE will be considered treatment emergent and assigned to the initial treatment period, unless the AE end month is not missing and before the month of the exposure start or the AE has a complete end date which is before the exposure start date.
- If the year of the AE start is after the year of exposure start, it will be assumed that the AE started on the 01 January and the AE will be assigned to the initial, maintenance, open-label or follow-up period accordingly.

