11.2 Reporting of adverse events

AEs reported by the subject or observed by the investigator must be recorded on the AE form of the CRF and should be described in the following manner:

The *AE term* must be in precise English medical terminology (i.e. not necessarily the exact words used by the subject). Whenever possible, a specific diagnosis should be stated (for example 'allergic contact dermatitis').

The *duration* of the AE must be reported by the start date and stop date of the event. In addition, it must be recorded whether the AE started prior to start of IMP.

AEs must be classified in terms of severity, causality and outcome according to the definitions in Appendix 3.

Action taken with trial treatment: Any action taken with IMP as a consequence of the AE must be recorded (dose not changed, dose reduced, dose increased, drug interrupted, drug withdrawn, not applicable, unknown).

Trial ID: LP0162-1325	Date: 14-Aug-2018	Version: 4.0
		Page 85 of 169

Other action taken: any other action taken as a result of the AE must be recorded (none, concomitant medication, concomitant procedure).

Withdrawn due to AE: it must be recorded whether the AE leads to withdrawal from the trial.

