12.3.7.1 Adverse events

AEs will be coded during the course of the trial according to Medical Dictionary for Regulatory Activities (MedDRA). AEs will be presented by preferred terms and primary system organ class (SOC).

Treatment-emergent AEs will be summarised, however, all AEs recorded during the course of the trial will be included in the subject data listings. An event will be considered treatment-emergent if started after the first use of IMP or if started before the first use of IMP (applicable if subject had a wash-out) and worsened in severity thereafter. The tabulations described in the following will only include the treatment-emergent events. In each of the tabulations, AEs will be defined by MedDRA preferred terms within primary SOC.

An overall summary of the number of treatment-emergent AEs, number (percentage) of subjects with any treatment-emergent AEs, SAEs, deaths, premature discontinuations from the trial due to AEs, treatment-related AEs and severe AEs will be presented.

The number of AEs and the number of subjects experiencing each type of AE will be tabulated by treatment group. The percentage of subjects with AEs in the initial treatment period will be compared between treatment groups by a chi-square test or Fisher's exact test (if expected cell count < 5).

The severity for each type of AE will be tabulated by treatment group.

The causal relationship to IMP for each type of AE will be tabulated by treatment group.

Related AEs are defined as AEs for which the investigator has not described the causal relationship to IMP as 'not related'. The number of related AEs and the number of subjects experiencing each type of related AE will be tabulated. The percentage of subjects with related AEs in the initial treatment period will be compared between treatment groups by a chi-square test or Fisher's exact test (if expected cell count <5).

SAEs and AESIs will be evaluated separately. A narrative for each SAE will be given. AESIs and AEs leading to withdrawal from trial will be tabulated and listed.

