completing the treatment period, and otherwise the date of permanent discontinuation of IMP for subjects not completing the treatment period. See also section 6.8.2 for further details.

For analysis of efficacy subjects will be included 'as randomised'.

For analysis of safety, if a subject is mistakenly given an experimental therapy other than that to which they were randomized, they should be analyzed 'as-treated', thus included in the group according to the therapy actually received by the subject. The below rules will be applied.

Subjects who received at least one dose of tralokinumab during the initial treatment period will be analysed in the tralokinumab treatment group. Although this may dilute the AE rate in the tralokinumab treatment group slightly by including in the denominator subjects who only received one dose of active treatment, it will ensure that no significant drug reactions to tralokinumab will erroneously be assigned to placebo.

Subjects in the maintenance safety analysis set will be analysed as follows:

Week 16 Tralokinumab responders will be displayed in tables for the maintenance period according to actual treatment defined as:

- Tralokinumab Q2W if
  - subject was randomised to Tralokinumab Q2W and at least one dose of active treatment was administered, or
  - subject was randomised to placebo, but more than half of the administered doses contained active treatment.
- Tralokinumab Q4W if
  - subject was randomised to Tralokinumab Q4W and at least one dose of active treatment was administered, or
  - subject was randomised to placebo but at least one and at most half of the administered doses contained active treatment.
- Placebo if only placebo doses were administered

By assigning subjects randomised to placebo who got at least one active treatment to the Q4W arm a potential safety signal in the Q2W group is not deflated.

Week 16 placebo responders will be displayed in the "Week 16 placebo responders / Placebo" column in summary tables, regardless of actual treatment received. Any deviations from the

Trial ID: LP0162-1325	Date: 20-May-2019	Version: 1.0
		Page 11 of 31

planned treatment regimen (i.e. if any active doses are given) will be described as protocol deviations.

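### SAP 6.8.3 counts an AE with an incomplete start date as treatment-emergent even when the CRF records that it began before IMP

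*SAP*

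**What the plan says.** SAP 6.8.3 (Incomplete recordings, Adverse events) covers two situations.

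- **Start day missing, month and year known.** If the month is that of exposure start, "the AE will be considered treatment emergent and assigned to the initial treatment period, unless the AE has a complete end date" that falls before exposure start. For a later month, "it will be assumed that the AE started on the first day of the month".
- **Start month missing, year known.** "If the year of the AE start is the same as the year of the exposure start, the AE will be considered treatment emergent" and placed in the initial period, unless the end month or a complete end date precedes exposure start. For a later year, "it will be assumed that the AE started on the 01 January".

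SAP 6.7.1 sends all incomplete AE start dates to these rules. For complete dates falling on the day of first dose, the same section counts only AEs that began after the dose.

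Protocol 11.2, on what is recorded for each AE, adds to the start and stop dates: "In addition, it must be recorded whether the AE started prior to start of IMP". Protocol 12.3.7.1 defines the term: "An event will be considered treatment-emergent if started after the first use of IMP", or if it began earlier and then worsened in severity.

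**The concern.** The trial collects the fact that decides whether an AE is treatment-emergent, and the SAP rule for incomplete dates does not look at it. The rule tests only whether the AE had already ended before exposure start. An AE that began in screening and was still ongoing at first dose passes that test and enters the treatment-emergent tables, even when the investigator recorded that it preceded IMP.

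Pre-dose AEs will be in the database. Protocol 11.1 starts collection at the first trial-related activity after consent, and Protocol 7.1 gives a screening period of 2 to 6 weeks. The tables affected include the initial-period percentages of subjects with AEs and with related AEs, which Protocol 12.3.7.1 tests between arms.

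**Working it through.** The documents state no figure on this point, so there is none to reproduce. The check is a trace of the rules, followed by illustrative shares.

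**1. Day missing, month of first dose.** Take first dose on 20 March 2018 and an ongoing AE dated March 2018, recorded as starting before IMP.
- SAP 6.8.3: same month and year as exposure start, no end date before it. Result: treatment-emergent, initial period.
- Protocol 12.3.7.1: started before first use of IMP. Result: not treatment-emergent unless it worsened.

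The two results differ, and the recorded item would have settled the matter.

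**2. Month missing, year of first dose.** The same AE dated only 2018 gives the same conflict.

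**3. Does the worsening clause rescue the rule?** No. Protocol Appendix 3 asks for a new AE record when severity worsens, so a worsened event has its own entry. The rule does not ask about worsening either.

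**4. How many possible onset days are pre-dose?** For one first-dose date,

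share = (collected days in the month before first dose) / (all collected days in the month).

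For 20 March:
- 14-day screening: collection runs 6 to 31 March, so 14/26 = 54%.
- 42-day screening: the whole month is covered, so 19/31 = 61%.

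Pooled over all 365 first-dose dates, taking each date and each onset day as equally likely (assumptions):

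| Incomplete date | Screening 14 days | Screening 42 days |
|---|---|---|
| Day missing, first-dose month: pre-dose share | 40% | 48% |
| Month missing, first-dose year: pre-dose share | 7% | 18% |
| Month missing, first-dose year: share after Week 16 | 45% | 40% |

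The first row ranges from 0% to 97% by first-dose date. These are shares of possible onset days, not of AEs. They include AEs that ended before dosing, which the rule excludes correctly.

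**5. The other imputation rules and the Week 16 switch.** First dose and Week 16 (Day 112) never fall in the same month, so the same-month rule cannot misplace a post-switch AE. The first-of-month, year-only and 01 January rules can. Take a placebo subject with first dose on 15 January 2018 who moves to open-label tralokinumab on 7 May 2018. An AE dated May 2018 is set to 1 May and counted under placebo. Under the same uniform assumption, 52% of the days in the switch month fall on or after the switch, while the 1st precedes the switch for 97% of first-dose dates.

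Under the planning rates in Protocol 7.2 and 12.1, the subjects who change treatment at Week 16 are:
- Placebo to open-label tralokinumab: 195 × (1 − 0.15) = 166. This is an upper figure: it uses EASI75 alone and ignores drop-out.
- Tralokinumab to open-label tralokinumab: 585 × (1 − 0.40) = 351.
- Tralokinumab to maintenance placebo: 585 × 0.40 × 1/5 = 47.

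The first group can have tralokinumab-period AEs counted under placebo. The second adds later AEs to the tralokinumab initial-period column. The third can have placebo-period AEs counted under tralokinumab.

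**The case against.** The best defence is that counting unknown onsets as treatment-emergent is a conservative and common default, and that few AEs will be affected. AEs are asked about at every visit (Protocol 11.1), visits are mostly two weeks apart, start and stop dates are required, and discrepant data are queried (Appendix 4D). All AEs are listed and each SAE has a narrative (Protocol 12.3.7.1). The point about size stands. The point about conservatism stands where the order of onset and dosing is unknown, but not where the CRF records it.

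A reader might go further and infer that the date rules push tralokinumab reactions into the placebo column, against the SAP's own safety principle. The documents do not support that reading, for three reasons.

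- The rules pull ambiguous AEs back in both arms, and the 47 responders re-randomised to placebo can move events the other way. No differential effect on the tested comparison follows.
- The sentence in SAP section 5 saying that "it will ensure that no significant drug reactions to tralokinumab will erroneously be assigned to placebo" concerns the column for a subject given the wrong treatment. It sets no rule for imputing dates.
- Sending ambiguous AEs to the later period would not be a clear improvement, since it could take AEs of tralokinumab subjects out of the initial-period column, which is the one tested.

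**Conclusion.** The narrow point holds on the text. For the two incomplete-date patterns, SAP 6.8.3 overrides a recorded pre-IMP onset and so conflicts with the treatment-emergent definition in Protocol 12.3.7.1. Nothing else in the SAP corrects it.

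It is a minor point. Probably a few events are involved, in both arms, so the main effect is noise in the initial-period tables and not a directional bias. No count can be derived, because the documents give neither the number of partial dates nor an AE rate. The percentages above rest on uniform first-dose and onset dates and on 14- or 42-day screening, and show only that pre-dose onset is a realistic possibility for such records. A one-sided shift towards placebo is not shown.

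**What to change.** Add one sentence to SAP 6.8.3: an AE with an incomplete start date that is recorded as having started before IMP is not treatment-emergent unless it worsened in severity after first dose. Keep the present default only where that item does not settle the order, for example because it is missing or contradicts the known part of the date.

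The first-of-month, year-only and 01 January rules need no change on this evidence.

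The cost is one sentence and one extra condition in the AE derivation, using an item Protocol 11.2 already requires. The classification then depends on that item being completed correctly, so contradictions with the known part of the date should be queried.
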